5.6 Data Analysis

Figure 3. CONSORT Diagram

5.6A. Power analysis and sample size for the RCT phase.

Based on annual rates of patients initiating EBPs for PTSD at each site, we estimate 1751 Veterans will be referred for EBPs over the recruitment period (27 months). Based on response rates for Project HomeFront, we anticipate 50% (n = 876) will be interested in research. See Figure 3 for recruitment flow. Estimates are conservative and incorporate Project HomeFront data, including that 8% will not have eligible SPs, 34% of Veterans will be unwilling to ask SPs to participate, and 20% of SPs will not be interested. To support recruitment success, we will also use study fliers and brochures strategically placed in appropriate clinic locations. We will contact patients until we reach 156 patients randomized (78 in each arm).

We expect to enroll 2 subjects per month, per site, during recruitment for a total n of 156 Veterans and 156 SPs.

Session attendance serves as the primary outcome. Analyses below indicate our proposed minimum n of 156 is sufficient to detect clinically meaningful differences between standard PE and family supported PE on Aim 1 and Aim 2 outcomes. Data analysis will take place at the Minneapolis VA Health Care System. Individuals involved in data analysis (quantitative and qualitative) will include [name] and Drs. [name], [name], [name], [name], and [name].

5.6A1. Aim 1. Preliminary Project HomeFront data indicate the average number of sessions attended is 7.30 ($SD = 4.45$). Seventy-eight participants in each arm yields 80% power to detect a two session difference between treatment conditions. A two session improvement corresponds to an effect size of ($d = 0.43$), slightly below conventions for a moderate effect size ($d = .50$). A greater sample size could detect smaller effects, but these are unlikely to be clinically meaningful. An alternative approach is to power the study based on a minimally

clinically significant increase in rates of treatment completion (e.g., at least 10%). However, given the increased power needed to detect change in a dichotomous outcome, this would not be feasible; we would need at least 692 subjects for 80% power.

5.6A2. Aim 2 (family supported PE will lead to greater reductions in PTSD symptoms than standard PE).

Power analyses are based upon our ability to detect a clinically meaningful difference between our two treatment conditions on PTSD symptom severity using the PCL.⁵ A five-point difference on the PCL is the minimal threshold for determining if an individual has responded to treatment (i.e., differences not due to chance); a ten point difference is the minimal threshold for clinically relevant differences.⁷ Smaller differences are unlikely be clinically meaningful. Analyses take into account our repeated measures, two-armed design and estimates of variance and auto-correlations between repeated PCL assessments from our prior work (Project HomeFront, Time 1 PCL SD = 12.16; Time 2 PCL SD = 14.8; Time 1 and Time 2 PCL, $r = .61$). Using a plausible range of auto-correlations ($r = .50\text{-.70}$) and standard deviation estimates (SD = 12.16-14.8), and assuming 20% missingness on posttreatment PCL scores ($n = 124$), we are sufficiently powered (80%) to detect a 4.1 to 5.8 point difference between treatment conditions on posttreatment PCL total scores ($d = .34\text{-.40}$). Analyses will rely on the latest version of the PCL (i.e., the PCL-5²). Data currently is unavailable translating clinically meaningful differences on the PCL to the PCL-5; however, preliminary work suggests the ranges described above will be similar for the PCL-5.²

5.6B. Data Analysis.

5.6B1. General Approach. The study is a two arm patient-level randomized superiority trial, nested within 3 sites, each with 4 providers. Analyses will consider this design structure and follow intent-to-treat methodology. First, we will examine the distribution of all study variables (data verification). Second, we will evaluate bivariate associations between condition assignment and study outcomes and covariates to determine unadjusted measures of effect and identify imbalance in baseline covariates. Due to randomization, we do not anticipate imbalances in baseline characteristics between groups, but we will adjust for any differences by including these variables as covariates. Third, we will examine the impact of missing survey items and adjust for their influence. After testing and identifying the mechanism underlying any missingness (MAR,NI), we will use the implied specific imputation methods to impute missing covariates and factors and generate five imputed data sets. Final analyses will include complete case analysis and an aggregated analysis based on the multiply imputed data.

5.6B2. Aims 1 and 2. After completing the above steps, we will test our hypothesis for Aim 1 using generalized linear mixed models. The number of sessions attended, within the assumed and appropriate fitted distribution, will be modeled with treatment and site as fixed effects and a random provider effect (clustering by provider). Analyses for Aim 2 will similarly use mixed models to examine differences between conditions on PCL-5 scores over time, modeling the treatment, time, and treatment by time effects. Secondary analyses will examine CAPS-5 scores and loss of diagnosis on the CAPS-5 (both PTSD diagnosis and subclinical PTSD diagnosis) to facilitate comparisons with existing and ongoing research on treatments for PTSD. We will also examine differences between conditions on PHQ-9, WHO-QOL, QRI, and CSQ-8 scores.

Analyses will follow the same general approach as Aim 1, with some exceptions. First, some indices are dichotomous (i.e., presence or absence of PTSD or subclinical PTSD diagnosis). Models will be fit using appropriate distribution and link functions (i.e. for binomial distribution and logit links for PTSD diagnosis; whereas mean group differences might fit a normal distribution). Second, unlike Aim 1, which relies on administrative data, Aim 2 outcomes rely on

self-report data, where some attrition is inevitable. Analyses will include examining group differences using available data, as well as analyses employing imputation as described above. To study the time-dependence of clinical outcomes, we will model the first-order transition probabilities of Markov chains (under treatment and control) with auto regressive random intercepts, random slope (provider), and fixed effects for treatment, site, sessions attended, and homework compliance. Lastly, we will explore indirect pathways from family supported PE to improved treatment outcomes through greater adherence (e.g., treatment condition → session attendance → PTSD symptoms), using approaches for testing indirect effects described below.

5.6B3. Aim 3. Quantitative data sources include primary and secondary study outcomes (addressed above) and Patient Screening Databases. Patient Screening Databases will be examined descriptively to answer Key Questions from Table 4. Interviews and Process Log entries will be examined using a rapid turn-around analytic approach (RTAP) for qualitative data.¹⁰² RTAP is a team-based method that can be used to obtain rich qualitative results in a brief amount of time. Interviews will be transcribed. The first step of analysis is data reduction (an analytic approach that sorts, focuses, and organizes data).¹⁰³ Drs. [name] and [name] will draft, field, and revise two templated forms. One for use by staff to summarize each interview transcript and a second to organize and summarize Process Log entries. [name] will then train and supervise staff on use of the final template. She will transfer summary points from templates into data matrices that organize points for each RE-AIM factor by population (i.e., Veteran, provider, leadership). The Qualitative Subgroup investigators will then meet to provide their impressions of the matrix contents. We will then develop tables listing 1) barriers/facilitators to implementation of family supported PE, 2) relevant findings from qualitative interviews, 3) relevant existing literature, 4) proposed implementation strategies, and 5) literature relevant to the proposed implementation strategies. Tables will also include, the degree to which barriers/facilitators are likely amenable to change, how conclusions may vary with subgroups (e.g. gender, racial/ethnic minorities, era), and how we anticipate implementation strategies will influence intervention fidelity.¹⁰⁴ [name] will create a final memo summarizing the findings and key themes that emerged.

5.6B4. Exploratory Aim. For this Aim, we will test if differences between family supported PE and standard PE are mediated by the key social influences targeted by family supported PE (e.g., treatment condition → family support for PE participation → session attendance). Mediators include weekly scores on the CEQ-PTSD⁹⁶ (SP report), SORTS⁹⁷ (SP report), and Support Checklist (Veteran report). Analytic approaches will be similar to Aim 1, with social influence variables incorporated as mediators. This basic mediation model is a special case of random effects structural modelling, where each equation will have random intercept and provider terms, adjusted for site fixed effects. Indirect effects for mediators treated as single summary scores will be directly tested using bootstrapped confidence intervals¹⁰⁵ to avoid the often-violated assumption underlying Sobel's (1982) method that the sampling distribution of the indirect effect is normal. Analyses will also examine differences between conditions on the rate and shape of change in key social influences.

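### The Aim 2 claim of 80% power for a 4.1 to 5.8 point posttreatment PCL difference does not follow from the stated SDs, correlations and n = 124; the Aim 1 effect size should read d = 0.45, not 0.43

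*Combined protocol and SAP*

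**What the plan says.** Section 5.6A2 (combined protocol and SAP) bases Aim 2 power on a prior project with two PCL assessments: "Time 1 PCL SD = 12.16; Time 2 PCL SD = 14.8", correlation .61. It then takes SDs from 12.16 to 14.8, correlations from .50 to .70 and 20% missing posttreatment scores (n = 124), and concludes that "we are sufficiently powered (80%) to detect a 4.1 to 5.8 point difference between treatment conditions on posttreatment PCL total scores", labelled d = .34 to .40. The same section gives its benchmark for relevance: "a ten point difference is the minimal threshold for clinically relevant differences". The text says that the repeated-measures design was taken into account. It does not give the number of occasions, the correlation structure, alpha or sidedness.

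Section 5.6B2 plans mixed models for the PCL-5, "modeling the treatment, time, and treatment by time effects".

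For Aim 1, section 5.6A states that "Session attendance serves as the primary outcome". Section 5.6A1 gives SD 4.45 for sessions attended, 78 per arm and 80% power for a two-session difference, and labels that difference d = 0.43.

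**The concern.** The quantity named for Aim 2 is a between-arm difference at posttreatment, and the inputs are two SDs and one correlation from two time points. The natural calculations from those inputs are a baseline-adjusted posttreatment comparison or a change-score (treatment-by-time) comparison. Neither returns 4.1 to 5.8 points at n = 124, and both need larger differences.

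The PCL-5 is the main Aim 2 outcome. If that comparison is null, readers will use the printed range to judge which effects the trial could have found. A range that is too favourable would lead them to rule out effects for which the trial had less than 80% power. With alpha and formula missing, they cannot check it. Separately, the printed Aim 1 effect size disagrees with the SD, difference and power in its own paragraph.

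**Working it through.** **Inputs.** From 5.6A2: SD 12.16 and 14.8; r = .50, .61 (observed) and .70; n = 124, so 62 per arm (156 × 0.8 = 124.8). From 5.6A1: SD 4.45, two sessions, 78 per arm. Alpha is not stated.

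**Fixing alpha from Aim 1.** d = 2/4.45 = 0.449. With 78 per arm and a two-sided 0.05 t-test, power is 79.7%, which matches the stated 80%. One-sided 0.05 would give 87%. Two-sided 0.05 is therefore used throughout. The Aim 1 sample size reproduces, but its label does not: at d = 0.43, 78 per arm has 76% power.

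**Formulas for Aim 2.** By noncentral t, the standardised difference detectable with 80% power at 62 per arm is 0.5072.
- Baseline-adjusted: SD × √(1 − r²) × 0.5072
- Change: SD × √(2(1 − r)) × 0.5072

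Examples: 12.16 × √0.51 × 0.5072 = 4.40; 14.8 × √0.75 × 0.5072 = 6.50.

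| SD | r | Adjusted (points) | Change (points) |
|---|---|---|---|
| 12.16 | .50 | 5.34 | 6.17 |
| 12.16 | .61 | 4.89 | 5.45 |
| 12.16 | .70 | 4.40 | 4.78 |
| 14.8 | .50 | 6.50 | 7.51 |
| 14.8 | .61 | 5.95 | 6.63 |
| 14.8 | .70 | 5.36 | 5.81 |

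**Lower limit, 4.1 points.** No stated pair of SD and r reaches it. In the best case (SD 12.16, r = .70), power at 4.1 is 74% adjusted and 67% as change. The stated d = .34 would need r of about .74 (adjusted) or .78 (change), both outside .50 to .70.

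**Upper limit, 5.8 points, at SD 14.8.** For r = .50, .61 and .70, power is about 70%, 78% and 86% adjusted, and 58%, 69% and 80% as change. To detect 5.8 points with 80% power, r must be about .635 (adjusted) or .70 (change). The observed r is .61.

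**The plan's own observed values.** Read Time 1 as baseline and Time 2 as posttreatment.
- Change SD = √(12.16² + 14.8² − 2 × .61 × 12.16 × 14.8) = 12.14; detectable difference 6.16 points, power at 5.8 points 75%.
- Adjusted SD = 14.8 × √(1 − .61²) = 11.73; detectable difference 5.95 points, power at 5.8 points 78%.

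Both differences exceed the stated upper limit.

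**Alternatives tried.**
- One-sided 0.05, baseline-adjusted: 3.90 to 5.76 points. The lower end still misses, and Aim 1 would no longer be at 80%.
- Mean over five occasions with AR(1) correlation: the variance factor is 0.445 at r = .50 and 0.616 at r = .70. This gives 4.11 points (SD 12.16, r = .50) and 5.89 points (SD 14.8, r = .70), or 4.08 and 5.84 with the normal approximation. It is the nearest match found.

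**Ten-point benchmark.** At SD 14.8 and r = .50, power is 99.1% adjusted and 96.2% as change.

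**The case against.** The strongest reply is that this is a gap in specification, not a miscalculation. The plan refers to repeated measures and auto-correlations, schedules the PCL-5 during treatment (5.5A.4), and models scores over time (5.6B2). A five-occasion AR(1) average, with the normal approximation, gives 4.08 and 5.84 points, which round to the printed limits. That may well be how the figures arose. But the match was found by search: the power section states neither five occasions nor AR(1). A time-averaged difference is also a different quantity from the posttreatment difference that the sentence names. Under that same model the baseline-adjusted posttreatment contrast would need about 5.9 to 7.4 points, so this reading does not rescue the sentence as written. It does mean that any replacement range depends on the model chosen, which must be stated.

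A second reply is that mixed models and imputation recover some information from Veterans without a posttreatment score. If all 78 per arm counted in full, the baseline-adjusted range would be about 3.9 to 5.8 points, and both stated limits would be met. Full recovery is unlikely, however, and 124 is the plan's own input.

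A third reply is that little depends on the point. That is largely right: Aim 2 is not primary, every figure in the table is below ten points, and a null result should be read from its confidence interval. This limits the consequence but does not make the stated figures correct.

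**Conclusion.** The concern holds. For the posttreatment contrast it names, the plan does not have 80% power at 4.1 to 5.8 points across its stated inputs. At the ends of the range the detectable difference is understated by 0.3 to 0.7 points with baseline adjustment (4.40 against 4.1; 6.50 against 5.8), or by 0.7 to 1.7 points as change (4.78 against 4.1; 7.51 against 5.8). This rests on two-sided 0.05, 62 per arm and one baseline plus one posttreatment score. Clustering by provider is not included. If a time-averaged formula was used, the error lies in the name of the contrast and the missing assumptions, and the sentence still needs correcting. The Aim 1 d = 0.43 is a label error only: two sessions, 78 per arm and 80% power are right.

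**What to change.** In 5.6A2, state alpha, sidedness, the number of PCL occasions, the covariance structure and the contrast. Then do one of the following:
- For a two-score posttreatment contrast at n = 124, restate the 80% power range as about 4.4 to 6.5 points (d .36 to .44) with baseline adjustment, or about 4.8 to 7.5 points (d .39 to .51) as change.
- If a time-averaged or other formula was used, give it and stop calling the result a posttreatment difference.

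In 5.6A1, change d = 0.43 to d = 0.45.

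The cost is wording only. The Aim 2 figures become slightly less favourable if the two-score contrast is kept. Enrolment and the planned analyses do not change.

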5.5 Study Evaluations

5.5A. Quantitative Data Collection (Aim 1, Aim 2, Exploratory Aim).

Except where indicated, data collection for the IC and RCT phase is identical. Aim 1 outcome variables will be obtained from Medical Records (attendance) and Provider Report (homework compliance). Aim 2 outcomes will be obtained from Baseline (week 0) and Posttreatment (16 weeks post-session 1) assessments of PTSD symptom severity, depression severity, quality of life, and relationship functioning. Aim 3 outcomes will be obtained from qualitative sources. Our Exploratory Aim outcomes will be obtained from Baseline, Posttreatment, and brief Weekly self-reports from Veterans and SPs. See below for measures.

5.5A.1 Aim 1. Aim 1 outcomes will be measured with methods drawn from Project HomeFront and our prior work coding session notes for PE/CPT treatment completion.⁵¹ PE attendance will be counted from review of Medical Records. Participants will have 'completed' PE when providers record they have successfully completed PE in a final session note. Providers will also be asked to log patient attendance and indicate the dates of attended sessions, missed sessions, and cancelled/rescheduled sessions. Homework compliance will be captured through patient observation by providers (Provider Report). Rating items were adapted from those used with Exposure and Response Prevention Therapy for Obsessive Compulsive Disorder (also a cognitive-behavioral exposure therapy).⁹³ Providers will also report on rates SP-provider contact weekly.

5.5A.2 Aim 2. Clinical outcomes for Aim 2 will be assessed through multiple forms (i.e., self-report and structured clinical interview), consistent with gold-standard methodology used in prior RCTs of PE and CPT. Baseline and posttreatment paper-and-pencil questionnaires will be completed by participants in both the RCT and IC phase of the study. Some participants in the IC phase will also receive structured interviews to allow the study team to implement all study procedures prior to beginning the RCT. IC participants will receive in-treatment assessments before sessions 2a and 2b to contribute to the intensive coaching and feedback providers receive for these early cases.

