For RCT phase, structured clinical interviews will take place at Baseline (week 0) and posttest (within 4 weeks of final session). Self reports/surveys will take place at Baseline (during week 0) and at posttreatment (during final session). For drop out Veteran participants, posttest surveys will be completed 16 weeks post-session 1 and the posttreatment clinical assessment will be done within 4 weeks of that posttest survey. For late treatment completers (i.e., treatment takes more than 16 weeks), all posttest surveys and post clinical interviews will be delayed but will be done no later than 24 weeks post-session 1.

For the IC phase, weekly surveys will be given for the first 2 weeks of treatment (session 2a, and 2b). For the RCT phase, weekly surveys will be given during weeks 2, 4, 5, 6, 8, 10 and 12 of treatment. For participants, the weekly surveys during week 2 and 8 will be lengthier and more thorough. All structured interviews (CAPS-5³ and SCID-5-CT)¹² will be administered by trained and supervised assessors who are blinded to condition. Assessors will be trained and supervised weekly by [name], a licensed clinical psychologist with expertise in conducting structured diagnostic clinical interviews and assessing and intervening with patients experiencing mental health crises. For mailed assessments, we will use CCDOR's well-established modified-Dillman protocol with repeated mailings and an incentive (incentive schedule described below).⁶ For surveys of Veterans with PTSD, our team's response rates

have ranged from 55% to 85%. Given the short interval between assessments, we will include a telephone call reminder and an offer telephone administration to optimize response rates.⁶

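### Section 5.6B1 lets a test of MAR versus non-ignorable missingness choose the imputation for Aim 2; observed data cannot make that choice reliably, the listed analyses are unranked, and no departure-from-MAR analysis is guaranteed

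*Combined protocol and SAP*

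**What the plan says.** Section 5.6B1 (General Approach) sets the missing-data rule: "After testing and identifying the mechanism underlying any missingness (MAR,NI), we will use the implied specific imputation methods". The imputation it describes names covariates and factors, in five data sets, and does not name outcomes. On reporting it says: "Final analyses will include complete case analysis and an aggregated analysis based on the multiply imputed data". Section 5.6B2 extends the rule. Having noted that Aim 2 depends on self-report and will lose some respondents, it says: "Analyses will include examining group differences using available data, as well as analyses employing imputation as described above".

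The Aim 2 model in 5.6B2 is "mixed models to examine differences between conditions on PCL-5 scores over time, modeling the treatment, time, and treatment by time effects". Section 5.5A.4 makes PCL-5 the main Aim 2 outcome, and section 3.0 frames the hypothesis as change from pre- to posttreatment.

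The sections differ on which PCL-5 scores count. Section 5.5A says "Aim 2 outcomes will be obtained from Baseline (week 0) and Posttreatment (16 weeks post-session 1) assessments of PTSD symptom severity", while 5.5A.4 also lists PCL-5 self-reports during treatment.

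Section 5.6A2 sizes Aim 2 "assuming 20% missingness on posttreatment PCL scores". Section 5.5A.2 gives the team's response rates in surveys of Veterans with PTSD as 55% to 85%.

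**The concern.** MAR and non-ignorable missingness differ only in how the chance of being missing relates to the unseen values. A data set can show that missingness is related to observed variables, which is evidence against MCAR. It does not show whether, given those variables, the missing scores differ from what the model predicts. A procedure that claims to decide this borrows its answer from an assumed distribution or selection model, so the choice of imputation would rest on that assumption.

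Three gaps follow for PCL-5. The data handling for the named mixed model is not ranked. A non-ignorable analysis appears only as one possible result of the test, so a reader may never see how far the missing scores would have to depart from MAR to change the conclusion. And whether during-treatment scores enter the model is unsettled, although the scores in the model define what MAR conditions on.

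**Working it through.** **Inputs.** 156 randomised, 78 per arm (5.6A). 20% missing, n = 124, SD 12.16 to 14.8, r = .50 to .70 with .61 observed, detectable difference 4.1 to 5.8 points, d = .34 to .40 (5.6A2). Assumed, because the documents give no value: two-sided 5%; two time points; no provider or site clustering; departure from MAR in one arm only, of 5 or 10 points.

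**Step 1: the plan's own figures.** 156 × 0.80 = 124.8, so n = 124 (62 per arm) reproduces. The detectable difference is (1.96 + 0.84) × SE, with

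- baseline-adjusted SE = SD × √((1 − r²) × 2/62)
- change-contrast SE = SD × √(2(1 − r) × 2/62)

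This gives 4.4 to 6.5 points with baseline adjustment and 4.7 to 7.5 with a change contrast. The stated 4.1 to 5.8 is not matched by these formulas. The plan does not give its own formula, so this is not called an error; 4.1 and 5.8 serve below only as example results. Since 4.1/12.16 = 0.34 and 4.1/14.8 = 0.28, the 4.1-point figure belongs with SD 12.16.

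**Step 2: can observed data tell the mechanisms apart?** One MAR truth and three non-ignorable truths were simulated on the same observed scores. The observed-case difference was −4.95 in all four. The full-population difference was:

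| Departure in the two arms | Full-population difference |
|---|---|
| 0 and 0 (MAR) | −4.96 |
| 5 and 5 | −4.96 |
| 5 and 0 | −3.96 |
| 10 and 0 | −2.96 |

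The identical observed data are built in; that is the argument. Any MAR model has non-ignorable counterparts that fit the observed data equally well.

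**Step 3: bias.** Bias in the arm difference = f₁d₁ − f₂d₂, where f is the missing share and d the departure in each arm.

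- One arm only, 20% missing: 0.20 × 5 = 1.0 point; 0.20 × 10 = 2.0 points.
- Equal shares and equal departures: 0.
- 10% versus 30% missing, common 10-point departure: 1.0 − 3.0 = −2.0 points.

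**Step 4: false-positive rate with no true difference.** P(|Z + bias/SE| > 1.96). The extremes over the plan's SDs and r are:

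| Case | SE | 5 points | 10 points |
|---|---|---|---|
| SD 12.16, r = .70, baseline-adjusted | 1.560 | 9.8% | 25.0% |
| SD 14.8, r = .50, change contrast | 2.658 | 6.6% | 11.7% |

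**Step 5: tipping point.** The departure at which a significant result is lost is (difference − 1.96 × SE)/0.20.

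- 5.8-point result: from (5.8 − 1.96 × 2.658)/0.20 = 2.95 to (5.8 − 1.96 × 1.560)/0.20 = 13.7, about 3 to 14 points.
- 4.1-point result at SD 12.16:

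| r | Adjusted SE | Tips at | Change SE | Tips at |
|---|---|---|---|---|
| .50 | 1.891 | 2.0 | 2.184 | not significant (1.96 × SE = 4.28) |
| .61 | 1.731 | 3.5 | 1.929 | 1.6 |
| .70 | 1.560 | 5.2 | 1.692 | 3.9 |

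During-treatment scores, if modelled, would change these figures by an amount the documents do not allow to be computed.

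**The case against.** The strongest reply is that the plan is not empty here. It names one model for PCL-5, follows intent to treat, foresees attrition, lists imputed as well as unimputed analyses, and mentions non-ignorable missingness. Selection and pattern-mixture models can be fitted, so a mechanism test can in some sense be carried out. That is fair, and the point is therefore that the test is unreliable, because its answer comes from the assumed model form.

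A reader might infer that three rival analyses compete. The documents do not support that count: complete case (5.6B1) and available data (5.6B2) are not defined as different and may be the same analysis. What is missing is a ranking between unimputed and imputed results.

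A reader might also infer that the trial's main result is at risk. It is not: 5.6A makes session attendance primary, and 5.6B2 describes it as administrative data.

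The sizes rest on assumed one-arm departures that the documents neither give nor rule out; this stands. Nor do the documents show that 45% missing (the complement of 55% response) is to be expected. Repeat mailings, reminder calls, telephone administration and a $50 incentive (5.5A.3) may do better than the earlier surveys. Missingness above 20% is possible, not forecast.

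**Conclusion.** The concern holds for Aim 2, and the plan should be changed. The rule in 5.6B1 cannot give a reliable choice between MAR and non-ignorable imputation, no ranking settles which PCL-5 result counts, and no departure-from-MAR analysis is assured.

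Under the stated assumptions the consequence at 20% missing runs from slight (about 7% false positives instead of 5%) to serious (25%), depending on the size of a one-arm departure, the SD, r and the contrast. That spread is the reason to prespecify the sensitivity analysis; it does not predict bias in this trial. The planned mixed model is itself sound under MAR, and nothing here shows that MAR will fail.

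**What to change.** 1. Delete the mechanism test from 5.6B1.
2. Name as the primary Aim 2 analysis the planned likelihood mixed model on all available scheduled PCL-5 scores (valid under MAR), with the arm contrast from pre- to posttreatment as in section 3.0. State whether during-treatment scores are included, and reconcile 5.5A with 5.5A.4.
3. Make the complete-case and multiply imputed analyses secondary, and say that the imputation covers the PCL-5 outcome as well as covariates.
4. Add a delta-adjusted (tipping-point) analysis by arm, run whatever the missingness looks like. Fix and justify the delta range before any outcome is compared by condition, which is the second step in 5.6B1. The documents define no unblinding date to tie it to.

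Optional, for precision only: replace covariates chosen by observed imbalance with a short prespecified list of baseline prognostic variables already collected, including the baseline value of each outcome that has one.

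The cost is SAP wording, a little programming, one extra sensitivity table and prior agreement on the delta range, plus a few degrees of freedom if the optional step is taken. No new data are needed.

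### Five imputed data sets leave the imputed Aim 2 test dependent on the random seed when the result is near the significance boundary; a larger number costs only computing time

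*Combined protocol and SAP*

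**What the plan says.** Under General Approach (5.6B1), the analysts will "impute missing covariates and factors and generate five imputed data sets". That sentence names covariates and factors, not outcomes. The paragraph ends: "Final analyses will include complete case analysis and an aggregated analysis based on the multiply imputed data". It does not say which of the two decides.

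The link to outcomes is in 5.6B2. Having noted that the Aim 2 measures are self-reported and subject to attrition, it states: "Analyses will include examining group differences using available data, as well as analyses employing imputation as described above". The only imputation described above is the five-data-set procedure, so five is the number that applies to the Aim 2 outcomes.

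On the amount of missing data, the Aim 2 power section (5.6A2) proceeds by "assuming 20% missingness on posttreatment PCL scores". Section 5.5A.2 says that the team's response rates in surveys of Veterans with PTSD "have ranged from 55% to 85" per cent. The plan gives no seed, no criterion for Monte Carlo error and no rule for raising the number of imputations.

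**The concern.** Multiple imputation draws random values for the missing scores, so a pooled estimate from a finite number of data sets carries simulation noise on top of sampling error. With few imputations and a sizeable share of the outcome missing, that noise can move a p-value across the significance threshold. Two analysts who follow the plan exactly, with different seeds, could then report different conclusions from the imputed analysis of PCL-5, which section 5.5A.4 makes the main Aim 2 outcome. Because no seed is set in advance, it could also be chosen after results are seen. None of this depends on which missing-data mechanism is assumed.

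**Working it through.** **Inputs.** From 5.6A: 156 randomized, 78 per arm; "Time 1 PCL SD = 12.16; Time 2 PCL SD = 14.8"; correlation .61; 20% missing; 80% power. From 5.6B1: m = 5. From 5.5A.2: response of 55 to 85%, so 100 − 85 = 15% to 100 − 55 = 45% missing. Assumed: two-sided 0.05, and a fraction of missing information (FMI) close to the missing fraction.

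**The plan's own figure.** 78 × 0.80 = 62.4, so 62 per arm and 2 × 62 = 124 observed. This matches the n = 124 in 5.6A2.

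**Monte Carlo error of the pooled estimate.** As a share of its standard error this is √(FMI/m).

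- FMI 0.20: √(0.20/5) = 0.20; √(0.20/20) = 0.10; √(0.20/50) = 0.063.
- FMI 0.45: √(0.45/5) = 0.30; √(0.45/20) = 0.15; √(0.45/50) = 0.095.

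In PCL points, the baseline-adjusted standard error with 62 per arm is 14.8 × √(1 − 0.61²) × √(2/62) = 14.8 × 0.792 × 0.180 ≈ 2.1. At m = 5 and 20% missing, the seed therefore moves the estimate with an SD of about 0.20 × 2.1 ≈ 0.42 points. The simulation below gave about 0.43.

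**Simulation of the t statistic.** The t statistic varies more than the estimate, because the pooled standard error also changes with the seed. Setup:

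- N = 156, with the SDs and correlation above.
- Posttreatment PCL missing completely at random, in equal numbers per arm.
- Normal-regression imputation from arm and baseline.
- Baseline-adjusted arm effect, pooled by Rubin's rules with Barnard-Rubin degrees of freedom.
- Each data set held fixed and re-imputed with 1,000 seeds, averaged over five data sets per setting.

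The simulated FMI was about 0.17, 0.22 and 0.45 at 15%, 20% and 45% missing. The SD column spans complete-case t values of 2.0, 2.3 and 2.8. The last value is the one expected at 80% power: 1.96 + 0.84 = 2.80.

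| Missing | m | SD of t between seeds | 95% seed range of p, t = 2.3 | Seeds losing significance, t = 2.3 | Same, t = 2.8 |
|---|---|---|---|---|---|
| 15% | 5 | 0.21–0.24 | 0.008–0.079 | 12.5% | 0.5% |
| 20% | 5 | 0.25–0.30 | 0.006–0.100 | 20.0% | 1.9% |
| 20% | 20 | 0.12–0.14 | 0.012–0.046 | 1.4% | 0.0% |
| 20% | 50 | 0.08–0.09 | 0.016–0.036 | 0.0% | 0.0% |
| 45% | 5 | 0.43–0.55 | 0.002–0.197 | 40.1% | 18.5% |
| 45% | 20 | 0.21–0.26 | 0.009–0.073 | 13.9% | 0.1% |
| 45% | 50 | 0.13–0.16 | 0.012–0.050 | 2.7% | 0.0% |

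A separate simulation with the same inputs put the loss at 20% missing, m = 5 and t = 2.3 at about 18%.

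**Sensitivity to FMI.** If FMI were only about 10%, the SD of t at m = 5 would be 0.16 to 0.18, and about 6% of seeds would lose significance at t = 2.3.

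**The case against.** Several points on the other side stand.

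- **Scope.** A reader might infer that the trial's main conclusion hangs on a seed. The documents do not support that. Session attendance is the primary outcome (5.6A) and comes from administrative data (5.6B2), so it is not itself imputed. Aim 2 is also analysed by a mixed model on available data, which has no seed. Only the imputed one of the two Aim 2 analyses is exposed.
- **Where five comes from.** It is tempting to read 5.6B1 as fixing five imputations for outcomes. Its sentence does not name outcomes; the case rests on the cross-reference in 5.6B2. That is the likelier reading, because the text just before it is about attrition.
- **Amount missing.** A reader might take 20% as a floor. It is the planning value. The past response rates imply 15 to 45%, which reaches below 20%, and they are not a forecast for this trial. Section 5.5A.3 adds incentives, repeated mailings, reminder calls and telephone completion, so 45% is a stress case.
- **FMI.** PCL-5 is also collected during treatment. An imputation model using those scores could lower the FMI: with an assumed correlation of .8 with posttreatment and complete in-treatment data, it falls to about 0.12 and the SD of t to about 0.18. The plan does not specify such a model, and dropouts may miss those surveys too.
- **Efficiency.** Five imputations give a relative efficiency of 1/(1 + 0.20/5) = 96% at FMI 0.20, and 1/(1 + 0.45/5) = 92% at 0.45. This is correct, so five is not an invalid choice. But efficiency describes the average variance of the estimate, not whether a single reported p-value can be reproduced.

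**Conclusion.** The point holds as a minor but worthwhile improvement. At the planned 20% missing, five imputations make the pooled Aim 2 t statistic vary between seeds with an SD of 0.25 to 0.30, about three times the 0.08 to 0.09 seen with 50. For a near-boundary result (t = 2.3), roughly one seed in five would lose significance. For a result of the size expected at 80% power, about one in fifty would. The sizes rest on an FMI close to the missing fraction, data missing completely at random, imputation from arm and baseline only, and a two-sided 0.05 level. The documents do not support a claim that the primary result or the available-data Aim 2 result is unstable.

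**What to change.** In 5.6B1, replace five with a larger stated number, for example 50. Twenty would largely suffice at 20% missing but not at 45%, and 50 covers the whole 15 to 45% range reasonably well. State in 5.6B1 that this number also applies to the Aim 2 outcomes, set the seed before outcome analysis begins, and report the Monte Carlo error of the imputed Aim 2 estimate. This changes one number and adds two sentences. The only cost is computing time: there are no new data and nothing changes for participants.
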